### 9.3.3 Removal of Subjects from Therapy or Assessment

The investigator may discontinue treating a subject with study treatment or withdraw the subject from the study at any time for safety or administrative reasons. The subject may decide to discontinue study treatment or withdraw from the study at any time for any reason. The reason for discontinuation will be documented. The investigator should confirm whether a subject will withdraw from study treatment but agree to continue protocol-specified, off-treatment study visits, procedures, and survival follow-up, or whether the subject will withdraw consent. If a subject withdraws consent, the date will be documented in the source documents.

Follow-Up Period will begin immediately after the final visit in subsequent TPC period. Subjects will be followed every 12 weeks for survival and will continue as long as the study subject is alive unless the subject withdraws consent. Subjects who do not take subsequent TPC will be followed for survival every 12 weeks after the lenvatinib Off-Treatment Visit of Lenvatinib Treatment Period.

All subjects will be followed for survival until death, except where a subject withdraws consent or the sponsor chooses to halt survival follow-up after completion of the primary study analysis.

## 9.4 Treatments

### 9.4.1 Treatments Administered

#### 9.4.1.1 Test Drug: Lenvatinib

Lenvatinib capsules will be administered orally, QD in continuous 28-day cycles. The starting dose of lenvatinib will be based on the subject's baseline BW as follows:

- BW  $\geq$ 60 kg — Lenvatinib 12 mg (taken as three 4-mg capsules) QD.
- BW  $<$ 60 kg — Lenvatinib 8 mg (taken as two 4-mg capsules) QD.

Study medication should be taken at approximately the same time each day in a fasting state or following a meal.

If a dose is missed and cannot be taken within 12 hours, then that dose should be skipped and the next dose should be taken at the usual time of administration.

Lenvatinib treatment will continue until disease progression, development of unacceptable toxicity, subject requests to discontinue, withdrawal of consent, or termination of the study

by the sponsor. The duration of lenvatinib treatment for each subject is estimated to be 6 to 8 months.

If holidays or personal schedules make administration impossible on the scheduled days, then administration should be resumed as soon as possible.

#### 9.4.1.1.1 DOSE REDUCTION AND INTERRUPTION OF LENVATINIB

Dose adjustments for management of intolerable toxicities will be made according to the guidelines provided in [Table 1](#).

**Table 1 Dose Modification and Treatment Discontinuation Guidelines for Management of Lenvatinib-Related Toxicity**

Study Treatment Dose Reduction and Interruption Instructions		
Non-Hematologic Toxicities		
Treatment-Related Toxicitya,b	Management	Dose Adjustment
Grade 1 or Tolerable Grade 2		
	Continue treatment	No change
Intolerable Grade 2c,d or Grade 3e,d		
First occurrence	Interrupt until resolved to Grade 0-1 or baseline	One-level reduction
Second occurrence (same toxicity or new toxicity)	Interrupt until resolved to Grade 0-1 or baseline	One-level reduction
Third occurrence f (same toxicity or new toxicity)	Interrupt until resolved to Grade 0-1 or baseline	One-level reduction
Fourth occurrence (same toxicity or new toxicity)	Interrupt until resolved to Grade 0-1 or baseline	Discuss with sponsor
Grade 4g: Discontinue Study Treatment		
Hematologic Toxicities and Proteinuria		
Treatment-Related Toxicitya	Management	Dose Adjustment
Grade 1 or Grade 2		
	Continue treatment	No change
Grade 3		
First occurrence	Interrupt until resolved to Grade 0-2 or baseline	No change
Second occurrence (same toxicity or new toxicity)	Interrupt until resolved to Grade 0-2 or baseline	One-level reduction
Third occurrence (same toxicity or new toxicity)	Interrupt until resolved to Grade 0-2 or baseline	One-level reduction
Fourth occurrence f (same toxicity or new toxicity)	Interrupt until resolved to Grade 0-2 or baseline	One-level reduction
Fifth occurrence (same toxicity or new toxicity)	Interrupt until resolved to Grade 0-2 or baseline	Discuss with sponsor
Grade 4		
First occurrence	Interrupt until resolved to Grade 0-2 or baseline	One-level reduction
Second occurrence (same toxicity or new toxicity)	Interrupt until resolved to Grade 0-2 or baseline	One-level reduction

Third occurrence f (same toxicity or new toxicity)	Interrupt until resolved to Grade 0-2 or baseline	One-level reduction
Fourth occurrence (same toxicity or new toxicity)	Interrupt until resolved to Grade 0-2 or baseline	Discuss with sponsor

Note: Grading according to Common Terminology Criteria for Adverse Events (CTCAE) v4.03.

AEs = adverse events, ALT = alanine aminotransferase, AST = aspartate aminotransferase, ULN = upper limit of normal

- a: An interruption of study treatment for more than 28 days (due to treatment-related toxicities) will require a discussion with the sponsor before treatment can be resumed. During treatment interruption, repeat AEs assessment at least every 7 days (until restarting administration).
- b: Initiate optimal medical management for nausea, vomiting, diarrhea and/or hypothyroidism prior to any study treatment, interruption, or dose reduction.
- c: Applicable only to Grade 2 toxicities judged by the subject and physician to be intolerable.
- d: For proteinuria, interrupt until Grade 0-2.
- e: Not applicable to abnormal clinical laboratory values that require no treatment (eg, sodium). Manage ALT, AST, and gamma-glutamyltransferase values  $10 \times$  ULN or higher as Grade 3.
- f: Please ignore this step for subjects who start at 8 mg once daily.
- g: Excluding laboratory abnormalities judged to be non-life-threatening, which should be managed as Grade 3.

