**Dose adjustments for management of toxicities will be made according to the guidelines provided in the table below.**

### Study Treatment Dose Reduction and Interruption Instructions

Dose reductions occur in succession based on the previous dose level (eg, 12, 8, and 4 mg/day, and 4 mg every other day for the subjects with initial BW  $\geq$ 60 kg). Any dose reduction below 4 mg every other day must be discussed with the sponsor. Once the dose has been reduced, it cannot be increased at a later date.

Non-Hematologic Toxicities		
Treatment-Related Toxicity a,b	Management	Dose Adjustment
Grade 1 or Tolerable Grade 2		
	Continue treatment	No change
Intolerable Grade 2c,d or Grade 3e		
First occurrence	Interrupt until resolved to Grade 0-1 or baseline	One-level reduction
Second occurrence (same toxicity or new toxicity)	Interrupt until resolved to Grade 0-1 or baseline	One-level reduction
Third occurrence f (same toxicity or new toxicity)	Interrupt until resolved to Grade 0-1 or baseline	One-level reduction
Fourth occurrence (same toxicity or new toxicity)	Interrupt until resolved to Grade 0-1 or baseline	Discuss with sponsor
Grade 4g: Discontinue Study Treatment		
Hematologic Toxicities and Proteinuria		
Treatment-Related Toxicity a	Management	Dose Adjustment
Grade 1 or Grade 2		
	Continue treatment	No change
Grade 3		
First occurrence	Interrupt until resolved to Grade 0-2 or baseline	No change
Second occurrence (same toxicity or new toxicity)	Interrupt until resolved to Grade 0-2 or baseline	One-level reduction
Third occurrence (same toxicity or new toxicity)	Interrupt until resolved to Grade 0-2 or baseline	One-level reduction
Fourth occurrence f (same toxicity or new toxicity)	Interrupt until resolved to Grade 0-2 or baseline	One-level reduction
Fifth occurrence (same toxicity or new toxicity)	Interrupt until resolved to Grade 0-2 or baseline	Discuss with sponsor
Grade 4		
First occurrence	Interrupt until resolved to Grade 0-2 or baseline	One-level reduction
Second occurrence (same toxicity or new toxicity)	Interrupt until resolved to Grade 0-2 or baseline	One-level reduction
Third occurrence f (same toxicity or new toxicity)	Interrupt until resolved to Grade 0-2 or baseline	One-level reduction
Fourth occurrence (same toxicity or new toxicity)	Interrupt until resolved to Grade 0-2 or baseline	Discuss with sponsor

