##### Grading of Proteinuria

- Grading of proteinuria according to CTCAE v4.03 will be based on the 24-hour urinary protein result. Management of lenvatinib administration will be based on the grade of proteinuria according to the Dose Modification Guidelines ([Table 1](#)).

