#### **9.7.1.8.1 EXTENT OF EXPOSURE**

The number of cycles/days on treatment, quantity of study drug administered, and the number of subjects requiring dose reductions, treatment interruption, and treatment discontinuation due to AEs will be summarized.

Additionally, the following data will be summarized: percentage of subjects that receive TPC, average dose intensity and relative dose intensity of lenvatinib treatment and TPC, and feasibility rate (defined as the percentages of subjects completing the first 2, 4, and 6 cycles of lenvatinib treatment without requiring dose reduction due to AE).

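### Footnote d in Table 1 links proteinuria to non-hematologic rows whose first Grade 3 dose action differs from that in the block naming proteinuria

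*Combined protocol and SAP*

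**What the plan says.** Table 1 in Section 9.4.1.1.1 has two blocks. In the non-hematologic block, one group of rows is headed "Intolerable Grade 2 c,d or Grade 3 e,d", and its first line is "First occurrence Interrupt until resolved to Grade 0-1 or baseline One-level reduction". Footnote d, marked on both grades in that heading, says "For proteinuria, interrupt until Grade 0-2".

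The lower block is headed "Hematologic Toxicities and Proteinuria". At Grade 1 or 2 it continues treatment at the same dose. Its first Grade 3 line is "First occurrence Interrupt until resolved to Grade 0-2 or baseline No change".

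The synopsis repeats both blocks and the footnotes, but its corresponding heading is "Intolerable Grade 2 c,d or Grade 3 e", with footnote d on Grade 2 only. The synopsis also says that a dose, once lowered, is not raised again.

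Section 9.4.1.1.3, under Grading of Proteinuria, says "Management of lenvatinib administration will be based on the grade of proteinuria according to the Dose Modification Guidelines" and points to Table 1 without naming a block. Section 9.7.1.8.1 summarizes dose reductions due to AEs, dose intensity, relative dose intensity and a feasibility rate, the percentage of subjects "completing the first 2, 4, and 6 cycles of lenvatinib treatment without requiring dose reduction due to AE".

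**The concern.** A footnote that says how to handle proteinuria within a group of rows presupposes that proteinuria is managed in those rows. Footnote d changes only the grade to which the event must resolve. It leaves the dose column alone, and that column shows a one-level reduction at the first occurrence. The lower block covers the same toxicity by name and gives a different dose action. A site reading Table 1 can therefore reach two answers for a first Grade 3 proteinuria.

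What is at stake is consistent handling of the subject, and then the lenvatinib exposure summaries, which count reductions. Under the synopsis rule against re-escalation, a difference at the first event would persist.

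**Working it through.** The plan has no figure to reproduce here. The check follows one event through each block.

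**First Grade 3 proteinuria, Table 1**

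| | Non-hematologic rows with footnote d | Block naming proteinuria |
|---|---|---|
| Interrupt until | Grade 0-2 | Grade 0-2 or baseline |
| Dose action | one level down | none |

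The resolution grades agree. The dose actions do not.

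**Successive Grade 3 events, 12 mg start.** The synopsis gives the dose levels as 12, 8 and 4 mg daily, then 4 mg every other day.

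| Occurrence | Non-hematologic rows | Block naming proteinuria |
|---|---|---|
| First | 8 mg | 12 mg |
| Second | 4 mg | 8 mg |
| Third | 4 mg every other day | 4 mg daily |
| Fourth | discuss with sponsor | 4 mg every other day |
| Fifth | – | discuss with sponsor |

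The two readings stay one level apart through the third occurrence. For an 8 mg start, assuming the same levels apply from 8 mg downward, the first event gives 4 mg against 8 mg.

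**Intolerable Grade 2 proteinuria.** Footnote d's condition is already met at Grade 2, so the instruction to interrupt has no content. What remains of the upper rows is a one-level reduction; the lower block continues treatment unchanged. This overlap is in both tables, since both mark Grade 2 with d.

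**Synopsis, Grade 3.** Footnote d is not on Grade 3 there, so no footnote ties a Grade 3 proteinuria to the upper rows. The Grade 3 conflict is specific to Table 1.

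**Grade 4.** Footnote d is not marked on the Grade 4 row in either table, so this point does not extend to it.

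**Effect on the summaries, per subject.**
- Feasibility rate: taking all of the approximately 100 treated subjects as the denominator (an assumption), one subject whose only reduction in the window depends on the reading moves the rate by 1/100 = 1 percentage point.
- Relative dose intensity: taking the starting dose as the reference (an assumption), days after resumption count as 8/12 = 67% rather than 100% for a 12 mg start, or 4/8 = 50% rather than 100% for an 8 mg start.

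The number of such subjects cannot be derived, because the documents give no proteinuria incidence.

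**The case against.** The strongest reply is that Table 1 already separates proteinuria by name. The lower block lists an action for each grade and occurrence, and a reader would ordinarily prefer the block that names the toxicity to a generic one. Section 9.4.1.1.3 fits that reading, since it ties management to the grade of proteinuria. The lower block works by grade alone, whereas the upper rows turn on tolerability at Grade 2. Footnote d itself states no dose action, and its emptiness at Grade 2 suggests a leftover rather than a working second rule. Footnote e also takes laboratory values that need no treatment out of the non-hematologic Grade 3 rows, which may narrow the overlap.

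Much of this stands. A reader might infer that Table 1 orders a one-level reduction for a first Grade 3 proteinuria. It does not say so; that action follows only if the footnote is taken to bring the rest of the row with it. Nor do the documents show that sites would in fact diverge, or that every intolerable Grade 2 event would be handled differently.

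The reply does not remove the inconsistency. No text gives the lower block precedence. If that block governs, footnote d has no function, because the block already states its own resolution grade. Footnote e does not mention proteinuria and is not attached to Grade 2. The synopsis and the body also mark the same row differently, although that mismatch is a single superscript in text read by program and should be checked against the source file.

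**Conclusion.** This is an internal inconsistency of low severity. In Table 1, footnote d implies that proteinuria belongs to rows whose first-occurrence dose action differs from the one in the block that names it, and the synopsis marks the footnote differently. Sites could act differently on the same event; how often cannot be estimated from the documents.

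The possible effect is limited to lenvatinib dose-reduction counts, dose intensity and the feasibility rate, all descriptive in a single-arm study. A reader might go further and see a threat to the primary result. The documents do not support that: under Section 9.7.1.1.1 the primary endpoint is the safety and tolerability of the treatment after lenvatinib, and this footnote does not directly affect it.

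The conclusion assumes that the footnote markers were read correctly from the source file and that no instruction outside these documents tells sites which block to use.

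**What to change.** Reconcile footnote d with the block that names proteinuria, and state which block governs, so that each proteinuria grade and occurrence has one dose action. Make the footnote markers identical in the synopsis table and Table 1. Which action applies is for the sponsor to decide; none is proposed here.

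The cost is a footnote correction in two tables, with no change to sample size, assessments or analyses. If subjects have already been managed under the current tables, list those with proteinuria-related dose changes, so that the exposure summaries can be read with the action actually taken.

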#### 9.4.1.1.2 MANAGEMENT OF HYPERTENSION

Hypertension is a recognized side-effect of treatment with drugs inhibiting VEGF signaling. Investigators should therefore ensure that subjects enrolled to receive treatment with lenvatinib have BP  $\leq 150/90$  mmHg at the time of study entry and, if known to be hypertensive, have been on a stable dose of antihypertensive therapy for at least 1 week before Cycle 1/Day 1. Early detection and effective management of hypertension are important to minimize the need for lenvatinib dose interruptions and reductions.

Regular assessment of BP should be conducted as detailed in the Schedule of Procedures/Assessments. Hypertension will be graded using CTCAE v4.03, based on BP measurements only (and not on the number of antihypertensive medications).

Only one BP measurement is needed for subjects with systolic BP  $< 140$  mmHg and diastolic BP  $< 90$  mmHg. If the subject's initial BP measurement is elevated (systolic BP  $\geq 140$  mmHg or diastolic BP  $\geq 90$  mmHg), the BP measurement should be repeated at least 5 minutes later. The mean value of these 2 measurements done at least 5 minutes apart is defined as one BP assessment. If the BP assessment (ie, the mean of the 2 BP measurements obtained at least 5 minutes apart) is elevated (ie, systolic BP  $\geq 140$  mmHg or diastolic BP  $\geq 90$  mmHg), a confirmatory BP assessment should be obtained at least 30 minutes later by performing 2 measurements at least 5 minutes apart (to yield a mean value).

Antihypertensive agents should be started as soon as elevated BP (systolic BP  $\geq 140$  mmHg or diastolic BP  $\geq 90$  mmHg) is confirmed on 2 assessments at least 30 minutes apart. One BP assessment is defined as the mean value of 2 measurements at least 5 minutes apart. The choice of antihypertensive treatment should be individualized to the subject's clinical circumstances and follow standard medical practice. For previously normotensive subjects, monotherapy with one of the classes of antihypertensives should be started when systolic BP  $\geq 140$  mmHg or diastolic BP  $\geq 90$  mmHg is first observed on 2 assessments at least 30 minutes apart. For those subjects already on antihypertensive medication, the dose of the current agent may be increased, if appropriate, or one or more agents of a different class of

antihypertensive should be added. For subjects with hypertension and proteinuria, treatment with an angiotensin-converting enzyme inhibitor or angiotensin-II receptor antagonist is preferred.

**Study drug should be withheld in any instances where a subject is at imminent risk to develop a hypertensive crisis or has significant risk factors for severe complications of uncontrolled hypertension (eg, BP  $\geq$ 160/100 mmHg, significant risk factors for cardiac disease, intracerebral hemorrhage, or other significant comorbidities). Once the subject has been on same hypertensive medications for at least 48 hours and the BP is controlled, study drug should be resumed as described below.**

Subjects with systolic BP  $\geq$ 160 mmHg or diastolic BP  $\geq$ 100 mmHg must have their BP monitored every 2 weeks (on Day 15 or more frequently as clinically indicated) until systolic BP has been  $\leq$ 150 mmHg and diastolic BP has been  $\leq$ 95 mmHg for 2 consecutive treatment cycles. If a new event of systolic BP  $\geq$ 160 mmHg or diastolic BP  $\geq$ 100 mmHg occurs, the subject must resume the Day 15 evaluation until systolic BP has been  $\leq$ 150 mmHg and diastolic BP has been  $\leq$ 95 mmHg for 2 consecutive treatment cycles.

The following guidelines should be followed for the management of systolic BP  $\geq$ 160 mmHg or diastolic BP  $\geq$ 100 mmHg confirmed on repeat measurements after 30 minutes:

- Continue study drug and institute antihypertensive therapy for subjects not already receiving antihypertensive medication.
- For those subjects already on antihypertensive medication, the dose of the current agent may be increased, if appropriate, or one or more agents of a different class of antihypertensive should be added.
- If systolic BP  $\geq$ 160 mmHg or diastolic BP  $\geq$ 100 mmHg persists despite maximal antihypertensive therapy, then study drug administration should be interrupted and restarted at a dose of 8 mg QD (one dose level reduction as specified in table above) only when systolic BP  $\leq$ 150 mmHg and diastolic BP  $\leq$ 95 mmHg and the subject has been on a stable dose of antihypertensive medication for at least 48 hours.
  - If systolic BP  $\geq$ 160 mmHg or diastolic BP  $\geq$ 100 mmHg recurs on the 8 mg QD dose despite optimal management of hypertension with antihypertensive medications (either by dose increase or the addition of a different class of antihypertensive), then study drug administration should be interrupted and restarted at a dose of 4 mg QD (one dose level reduction as specified in the table above) only when systolic BP  $\leq$ 150 mmHg and diastolic BP  $\leq$ 95 mmHg and the subject has been on a stable dose of antihypertensive medication for at least 48 hours.
  - If systolic BP  $\geq$ 160 mmHg or diastolic BP  $\geq$ 100 mmHg recurs on the 4 mg QD dose despite optimal management of hypertension with antihypertensive medications (either by dose increase or the addition of a different class of antihypertensive), then study drug administration should be interrupted and a restart of study medication should be discussed with the sponsor.

The following guidelines should be followed for the management of Grade 4 hypertension (life-threatening consequences):

- Institute appropriate medical management
- Discontinue study drug.

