- h: Assessments will include vital signs (resting BP, heart rate, respiratory rate, and body temperature), and weight measured at Screening, Baseline, Day 1 and Day 15 of every cycle, lenvatinib Off-Treatment visit in Treatment Period 1, and at week 2, week 4, and week 8 ( $\pm$ 1 week) in TPC period. A TPC baseline assessment should be performed unless the lenvatinib Off-Treatment visit is completed  $\leq$ 7 days prior to the first TPC treatment. One BP assessment is defined as the mean value of 2 measurements at least 5 minutes apart. If the BP assessment is elevated (systolic BP  $\geq$ 140 mmHg or diastolic BP  $\geq$ 90 mmHg), a confirmatory BP assessment at least 30 minutes later should be obtained by performing 2 measurements (at least 5 minutes apart) to yield a mean value. Starting dose is determined based on measurement of body weight at the Baseline Visit. Subsequent measurements of body weight not relevant for dose determination. See dose adjustment table for management of hypertensive subjects.
- i: Subjects with systolic BP  $\geq$ 160 mmHg or diastolic BP  $\geq$ 100 mmHg must have their BP monitored every 2 weeks (on Day 15) or more frequently as clinically indicated until systolic BP has been  $\leq$ 150 mmHg and diastolic BP has been  $\leq$ 95 mmHg for 2 consecutive treatment cycles. If a new event of systolic BP  $\geq$ 160 mmHg or diastolic BP  $\geq$ 100 mmHg occurs, the subject must resume the Day 15 evaluation until systolic BP has been  $\leq$ 150 mmHg and diastolic BP has been  $\leq$ 95 mmHg for 2 consecutive treatment cycles.  
Urine dipstick testing for subjects with proteinuria  $\geq$ 2+ should be performed every 2 weeks (on Day 15) or more frequently as clinically indicated until the results have been 1+ or negative for 2 consecutive treatment cycles. If a new event of proteinuria  $\geq$ 2+ occurs, the subject must resume the Day 15 urine dipstick testing for evaluation of proteinuria until results are 1+ or negative for 2 consecutive treatment cycles.  

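### The 8 mg hypertension restart dose is no reduction for subjects who start lenvatinib at 8 mg, and the withhold and continue rules have no stated order

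*Combined protocol and SAP*

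**What the plan says.** Section 9.4.1.1.2 (Management of Hypertension) and the matching part of the synopsis carry the same text.

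- **Restart after persistent hypertension (third bullet).** If BP stays at or above 160 systolic or 100 diastolic on maximal treatment, drug is "interrupted and restarted at a dose of 8 mg QD (one dose level reduction as specified in table above"). If it recurs on 8 mg, drug is stopped and "restarted at a dose of 4 mg QD (one dose level reduction as specified in the table above"). Recurrence on 4 mg goes to discussion with the sponsor.
- **Starting dose.** Section 9.4.1.1 starts subjects of 60 kg or more at 12 mg daily and lighter subjects at 8 mg daily.
- **Dose ladder.** The synopsis dose-reduction instructions step down from the previous level (12, 8, 4 mg daily, then 4 mg every other day, illustrated for subjects of 60 kg or more) and do not allow a reduced dose to be raised again.
- **Withhold rule (bold paragraph).** "Study drug should be withheld in any instances where a subject is at imminent risk to develop a hypertensive crisis". The rule also covers subjects with important risks of serious harm from uncontrolled BP. The examples open with a BP of at least "160/100 mmHg, significant risk factors for cardiac disease, intracerebral hemorrhage, or other significant comorbidities". After 48 hours on the same antihypertensives, and when "the BP is controlled, study drug should be resumed as described below".
- **Continue rule (first bullet).** For a confirmed systolic of at least 160 or diastolic of at least 100 mmHg: "Continue study drug and institute antihypertensive therapy for subjects not already receiving antihypertensive medication".
- **Other pointers.** Table 3, footnote h, adds: "See dose adjustment table for management of hypertensive subjects". Table 1 handles a first intolerable Grade 2 or a Grade 3 non-hematologic toxicity with "Interrupt until resolved to Grade 0-1 or baseline" and a one-level reduction.

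**The concern.** The third bullet gives a fixed milligram dose and then describes it as one step down. That holds only for someone taking 12 mg. A subject who starts at 8 mg and whose BP stays high on full treatment could be restarted at the very dose on which the BP could not be controlled.

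The bold paragraph and the first bullet sit a few lines apart and can both be met by one reading, with opposite instructions about the drug. The pointer for restarting after a withhold leads to bullets that cover other situations.

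Hypertension is a toxicity that the section itself describes as recognized for drugs of this class. Different sites could act differently on the same subject, and the Treatment Period 1 summaries of interruptions, reductions, dose intensity and feasibility rate would then partly reflect how each site read the text.

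**Working it through.** The plan gives no figure to reproduce here, so the check applies its rules to specific cases.

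**1. Restart dose in the third bullet.** Inputs: starting doses from 9.4.1.1 and the ladder from the synopsis.

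| Dose when BP persists | Restart by the number | Restart by the parenthesis | Gap |
|---|---|---|---|
| 12 mg | 8 mg | 8 mg (12 to 8 is one level) | 0 |
| 8 mg | 8 mg (no level) | 4 mg (8 to 4 is one level) | 8 − 4 = 4 mg/day; 4/8 = 50% |

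The two halves of the sentence agree for a 12 mg starter and disagree for an 8 mg starter. Table 1 lists no milligram levels, so the table that the parenthesis cites does not settle it. The synopsis ladder, which steps from the previous level, gives 4 mg. The same mismatch reaches a 12 mg starter already reduced to 8 mg for another toxicity.

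**2. Events needed to reach 4 mg, for an 8 mg starter.** By the number, two: BP persists (restart at 8 mg), then recurs on 8 mg (restart at 4 mg). By the parenthesis, one.

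**3. Effect on the feasibility rate.** Section 9.7.1.8.1 counts subjects who complete 2, 4 and 6 cycles with no dose reduction due to an AE. A subject restarted at 8 mg can stay in the numerator; one restarted at 4 mg cannot. If all 100 planned subjects are in the denominator (assumption), each such subject moves the rate by 1/100 = 1 percentage point.

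**4. Withhold or continue.** Take an untreated subject with a confirmed 165/105 mmHg.

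- Bold paragraph: 165 ≥ 160 and 105 ≥ 100, so the BP example is met: withhold.
- First bullet: systolic ≥ 160 (and diastolic ≥ 100), no antihypertensive yet: continue and treat.

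No sentence ranks the two. A reading of 165/85 meets the first bullet but not clearly the 160/100 example, so the clear overlap is narrower than the first bullet's range.

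**5. Restart after a first withhold.** The bullets below the bold paragraph give doses only for BP that persists on maximal treatment or recurs on 8 mg. Footnote h of Table 3 leads to Table 1, which pairs a first interruption with a one-level reduction, but the bold paragraph cites neither. Restarting at the same dose rather than one level lower differs by 4 mg/day: 4/12 = 33% for a 12 mg starter, 4/8 = 50% for an 8 mg starter.

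**The case against.** The best defence is that intent is readable throughout. The third bullet was evidently written with 12 mg starters in mind, and its parenthesis, the sub-bullet taking subjects from 8 to 4 mg, and the synopsis ladder all point an 8 mg starter to 4 mg. The bold paragraph has its own condition, high risk of crisis or severe complications, with 160/100 only an illustration; it reads naturally as a high-risk exception to a routine of continuing and treating, which fits the section's stated wish to limit interruptions. Table 1 can supply a restart dose. Grade 4 hypertension has a separate and clear rule.

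Much of this stands. A reader might infer that the withhold and continue rules flatly contradict each other. The documents do not support that: the override reading is reasonable, and what is missing is the sentence that says so. A reader might also infer that no restart dose exists after a first withhold. That too goes too far: one can be reached through Table 3 and Table 1, so the cross-reference is incomplete rather than the dose absent.

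The defence does not rescue the third bullet. The milligram figure is what a site acts on, it is wrong for a defined weight group, and the sub-bullet that reaches 4 mg is worded for recurrence on 8 mg, not for first persistence on a starting dose of 8 mg.

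**Conclusion.** The third bullet is wrong as written for subjects under 60 kg: the number gives no reduction, while the parenthesis and the ladder give 4 mg, a difference of 4 mg/day or 50%. This rests on applying the synopsis ladder to lighter subjects, which its step-from-previous-level wording supports although its example is for 60 kg or more.

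The order of the withhold and continue rules, and the restart dose after a first withhold, need clarification rather than correction. A reader might infer that the remedy is to strike 160/100 from the examples, or to impose a one-level reduction after every first withhold. The documents settle neither. The first would remove the only numeric anchor in a bold safety rule; the second would make a precautionary hold lower the dose permanently, because reductions cannot be reversed. Both are clinical decisions.

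The documents give no rate of severe hypertension and no weight distribution, so the number of subjects affected cannot be stated. The effect stays within lenvatinib dosing safety and the descriptive Treatment Period 1 exposure summaries. The primary endpoint (safety of the subsequent treatment) and OS, PFS and TTP keep the same definitions and analyses.

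**What to change.** 1. In the third bullet of 9.4.1.1.2 and of the synopsis, replace the 8 mg figure and its parenthesis with: *one dose level below the current dose (12 to 8 mg, or 8 to 4 mg)*. The sub-bullets on recurrence at 8 mg and at 4 mg can stay as they are.
2. Ask the sponsor's medical team to add, in both places, one sentence saying which of the bold paragraph and the first bullet prevails, and whether a BP of 160/100 mmHg alone triggers withholding.
3. Ask the same team to state the restart dose after a first withhold (same dose or one level lower), bearing in mind that a reduction is permanent, and to put it where the bold paragraph points.

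The cost is a few words in two places, with no change to data collection, endpoints or sample size. Because the text bears on subject safety, section 11.1 requires submission to health authorities and IRB/IEC approval. The changes could travel with the next amendment.
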